8.5.3.7 Adverse Events of Special Interest

The sponsor has developed a list of AEs of Special Interest for the BMS-986036 program based on the known biologic class effects, the mechanism of action, and clinical study data. These will include the following:

- Injection site reactions
- Gastrointestinal events
 - Diarrhea, frequent bowel movements, nausea, vomiting, abdominal pain
- Bone-related events
 - Osteoporosis, osteopenia, bone and joint injuries, fractures (except tooth fracture), endocrine abnormalities of gonadal function not elsewhere classified (NEC),

hyperparathyroid disorders, hypoparathyroid disorders, parathyroid disorders NEC, parathyroid analyses, metabolic bone disorders, vitamin D abnormal, vitamin D decreased, vitamin D deficiency, and miscellaneous events related to bone density

8.5.3.8 Bone Safety by DXA

Potential effects of BMS-986036 on BMD will be evaluated by DXA scans of the hip (including femoral neck) and spine that will be performed during the Screening Period and at the Week 48 Visit (or ET, if applicable) as indicated in the Schedule of Activities ([Section 1](#)). Participants will return for a follow-up DXA assessment 6 months (1 month is defined as 4 calendar weeks) after the Week 52/PTFU Visit. DXA may be performed within a window of ± 7 days of the scheduled Week 48 (or ET, if applicable) Visit and within a window of ± 14 days of the scheduled 6-month follow-up visit. DXA scans will be evaluated by central reading. Acquisition guidelines, instructions on calibration and the handling and submission of DXA scans are included in the Imaging Laboratory Manual. Note that at least one of the requested anatomic sites (hip [including femoral neck] or spine) must be evaluable for participants to be eligible for the study (See [Section 8.3.2](#)).

For participants prematurely discontinuing study medication DXA scans should be conducted at the ET Visit only if the participant has completed at least the Week 16 Visit. If a participant has not completed at least Week 16, the follow-up DXA scan at 6 months after PTFU Visit should also not be performed.

8.5.4 Laboratory Assessments

Participants should not administer study medication on the days of clinic visits until after all laboratory samples have been collected (see [Table 8](#) below). Blood samples will be collected according to the schedule in Section 1. In addition, a number of hematology and blood chemistry values collected as part of the safety laboratory assessments will also be used to determine FIB4 index, APRI, and NAFLD Fibrosis Scores according to the schedule in Section 1.

Safety (hematology, blood chemistry, and urinalysis), efficacy, and exploratory laboratory assessments to be conducted during the study are listed in Table 8 below. The schedule for collection of samples for each assessment is in Section 1. Laboratory assessments will be conducted by central or specialty laboratories. Additional details on the collection, processing, and submission of samples for laboratory assessments are in the Study Laboratory Manual. If clinically indicated, repeat laboratory testing may be performed at a local lab.

Investigators must document their review of each laboratory safety report. A central laboratory will perform the safety analyses and will provide reference ranges for these tests. Results of clinical laboratory tests performed during Screening must be available prior to dosing.

In addition to those detailed assessments outlined in Table 8 below, serum, plasma and urine may be assayed for exploratory markers associated with liver, fibrosis, [REDACTED] or

metabolic syndrome disease including markers associated with the BMS-986036 target pathway or with organs or pathways impacted by FGF21.

Urine or serum samples will be collected for pregnancy testing for WOCBPs. A negative serum pregnancy test is required during Screening. After the Screening Period, urine pregnancy testing will be conducted instead of serum testing at any site where it is allowed by the IRB/EC committee overseeing study conduct at that site. Women who are considered postmenopausal will have follicle-stimulating hormone testing performed during Screening.

Urine samples to test for drugs of abuse will be collected during Screening.

Repeat assessments for any laboratory assessment will be permitted according to the investigator's clinical judgment.

Table 8 Laboratory Assessments


ELF Assay (to be collected at Day 1, Week 24, Week 48, and ET [if applicable]). Participants will fast for 8 hours prior to collection of blood samples for these assessments:
 
• Hyaluronic acid• Procollagen 3 amino terminal peptide• Tissue inhibitor of metalloproteinases 1 (TIMP-1)

Laboratory Metabolic Markers (to be collected at Screening, Day 1, Week 24, Week 48, and ET [if applicable]). Participants will fast for 8 hours prior to collection of blood samples for these assessments:
 
• Low-density lipoprotein cholesterol• High-density lipoprotein cholesterol• Triglycerides• Plasma glucose – Also used for NAFLD Fibrosis Score.• Plasma insulin• Hemoglobin A1c – also to be collected at Long Term Immunogenicity Follow Up Visits as applicable (see Section 8.5.3.6)

Hepatitis Assessments (to be collected at Screening only- see Appendix 3 for diagnosis and exclusion criteria):
 
• Hepatitis B core antigen antibody• Hepatitis B surface antigen antibody• Hepatitis B surface antigen• Hepatitis B virus DNA• Hepatitis C virus antibody• Hepatitis C virus RNA

Pregnancy Testing (to be collected at each visit through the Week 52/PTFU Visit):
 
• Serum or urine β-HCG. Women of childbearing potential only. Serum β-HCG to be collected at Screening and serum or urine β-HCG to be collected thereafter according to local laws and regulations and Institutional Review Board/Ethics Committee requirements)• Follicle-stimulating hormone (Screening only for postmenopausal women)

Hematology (to be collected at each visit through the Week 52/PTFU Visit):
 
• Complete Blood Count
◦ White blood cells, including differential◦ Red blood cells

- Hemoglobin
- Hematocrit
- Platelet count – *Also used for FIB4, APRI, and NAFLD Fibrosis Score.*
- Mean corpuscular hemoglobin (MCH)
- Mean corpuscular hemoglobin concentration (MCHC)
- Red cell distribution width (RDW)
- Prothrombin time
- Partial thromboplastin time
- International normalized ratio

Blood Chemistry (to be collected at each visit through Week 52/PTFU and at Long-Term Immunogenicity Follow-Up Visits as applicable [see Section 8.5.3.6]):

- AST – *Used as both safety and efficacy endpoints. Also used for FIB4, APRI, and NAFLD Fibrosis Score*
- ALT – *Used as both safety, efficacy endpoints, and for FIB4, APRI, and NAFLD Fibrosis Score*
- Serum glucose
- Total bilirubin
- Indirect bilirubin
- Alkaline phosphatase
- Lactate dehydrogenase
- Creatinine
- Blood Urea Nitrogen
- Uric acid
- Total Protein
- Albumin – *Also used for NAFLD Fibrosis Score.*
- Sodium
- Potassium
- Chloride
- Carbon dioxide
- Calcium
- Phosphorus
- Glomerular filtration rate

Urinalysis (to be collected at each visit through the Week 52/PTFU Visit):

- pH
- Specific gravity
- Protein [REDACTED]
- Glucose
- Ketones
- Blood
- Leukocyte esterase
- Nitrite
- Creatinine [REDACTED]
- Albumin [REDACTED]
- Microscopic examination (only to follow-up abnormal findings)
- Drug Screen (Screening only)

Immunogenicity (to be collected at Day 1 and each subsequent visit through the Week 52/PTFU Visit and at Long-Term Immunogenicity Follow-Up Visits as applicable [see Section 8.5.3.6]):

- Serum anti-BMS-986036 antibody
- Serum anti-FGF21 antibody

PRO-C3 (to be collected at Screening, Day 1, Week 4, Week 8, Week 12, Week 24, Week 48, ET [if applicable], and Week 52/PTFU). Participants will fast for 8 hours prior to collection of blood samples for these assessments:

- N-terminal type 3 collagen propeptide (PRO-C3) – Will include blood collection for additional serum for new or improved assays

Adiponectin (to be collected at Screening, Day 1, Week 4, Week 8, Week 12, Week 24, Week 48, ET [if applicable], and Week 52/PTFU). Participants will fast for 8 hours prior to collection of blood samples for these assessments

Plasma and Serum for disease, target and drug effect biomarkers (to be collected at Day 1, Week 4, Week 8, Week 12, Week 24, Week 48, ET [if applicable], Week 52/PTFU, and 6 months after Week 52/PTFU). Participants will fast for 8 hours prior to collection of these samples

Gene Expression (to be collected at Screening, Day 1, Week 4, Week 8, Week 12, Week 24, Week 48, ET [if applicable], and Week 52/PTFU):

- Whole blood for RNA analysis (broad and/or directed gene expression profiling)

Micro RNA (miRNA) (to be collected at Screening, Day 1, Week 4, Week 8, Week 12, Week 24, Week 48, ET [if applicable], and Week 52/PTFU)

[REDACTED]; ALT = alanine aminotransferase; APRI = AST-Platelet Ratio Index; AST = aspartate aminotransferase; DNA = deoxyribonucleic acid; β -HCG = beta human chorionic gonadotropin; ELF = Enhanced Liver Fibrosis; ET = early termination; FGF21 = fibroblast growth factor 21; FIB4 = Fibrosis 4 Index; NAFLD = nonalcoholic fatty liver disease; NAS = NAFLD Activity Score; NASH = nonalcoholic steatohepatitis; PTFU = Post-Treatment Follow-up; RNA = ribonucleic acid;

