8.3.9 Withdrawal of Participants

8.3.9.1 Discontinuation of Study Medication

Participants MUST discontinue investigational product (IP) (and non-investigational product [non-IP] at the discretion of the investigator) for any of the following reasons.

- Participant's request to stop study medication. Participants who request to discontinue study medication will be expected to complete an ET Visit and subsequent follow-up visits/procedures per the Schedule of Activities (e.g., Week 52/PTFU; Section 1). The only exception to this is when a participant specifically withdraws consent for any further contact with him/her or persons previously authorized by participant to provide this information. Participants' withdrawal of consent should be explained in detail in the medical records by the investigator as to whether the withdrawal is from further treatment with study medication only or also from study procedures and/or ET, Week 52/PTFU Visit, etc. (see [Section 8.3.9.2](#))
- Any clinical AE, laboratory abnormality or intercurrent illness, which, in the opinion of the investigator, indicates that continued participation in the study is not in the best interest of the participant
- The participant experiences a major bone fracture or is diagnosed with osteoporosis that requires treatment
- Abnormal liver tests as defined in [Section 8.5.3.1](#)
- On 2 consecutive visits (at least 2 weeks apart), a participant has an eGFR < 30 mL/min/1.73 m², according to the *Modification of Diet in Renal Disease Study* equation
- If there is a significant protocol violation. The violation should be discussed with the medical monitor prior to discontinuing study medication
- Loss of ability to freely provide consent through imprisonment or involuntary incarceration for treatment of either a psychiatric or physical (e.g., infectious disease)

illness (Note: Under specific circumstances, a participant who has been imprisoned may be permitted to continue as a participant. Strict conditions apply, and sponsor approval is required.)

- The participant becomes pregnant (study medication must be discontinued immediately)

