8.5.1 Efficacy Assessments

Every effort must be made to ensure that the same evaluator(s) complete the assessment for each participant. If the evaluator(s) is unable to complete the evaluation, then a qualified individual with overlapping experience may perform the evaluation. Documentation of who performed the evaluation is to be recorded in source documents. Assessments should be performed at approximately the same time of day throughout the duration of the study. Baseline assessments must be performed prior to dosing with study medication. Procedures not specified in the protocol that are part of standard care may be performed if they do not interfere with study procedures; any data arising from such procedures are not to be reported in the eCRF.

All efficacy assessments will be completed prior to study medication administration. Participant questionnaires will be administered electronically, and information gathered electronically (i.e., electronic patient-reported outcome) will serve as the source document where possible.

The following procedures or tools will be used to assess participant's disease activity during the study (see the Schedule of Activities in [Section 1](#)):

- Liver biopsy (see [Section 8.5.1.1](#)) submitted to the central pathologist at Screening, and at Week 24 or the ET Visit, if applicable
 - Histological assessments of fibrosis stage and NASH activity
 - Assessments of CPA and fat in stained tissue by morphometry
 - Assessments of fibrosis using digital pathology
- Noninvasive measures of fibrosis and/or cirrhosis
 - Noninvasive scores of hepatic fibrosis (see [Section 8.5.1.2](#)) (AST-Platelet Ratio Index [APRI], Fibrosis 4 [FIB4] Index, Enhanced Liver Fibrosis [ELF] Score, NAFLD Fibrosis Score) at Day 1, Week 24, and Week 48 (or the ET Visit, if applicable)
 - Liver stiffness as determined by MRE (see [Section 8.5.1.3](#)) at Screening, Week 24, and Week 48 (or the ET Visit, if applicable)
- Hepatic fat fraction as determined by MRI-based proton density fat fraction (PDFF; see [Section 8.5.1.3](#)) at Screening, Week 24, and Week 48 (or the ET Visit, if applicable)
- Physical metabolic assessments (see [Section 8.5.1.5](#)) at Screening, Day 1, Week 24, and Week 48 (or the ET Visit, if applicable)
 - Body weight
 - Body mass index (BMI)
 - Waist circumference
- Laboratory Metabolic Assessments (see [Section 8.5.1.5](#)) at Screening, Day 1, Week 24, and Week 48 (or the ET Visit, if applicable)
 - Lipids (LDL, HDL, TGs)

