9.4.4 Exploratory Endpoints

- Quantitative measurements of fibrosis and fat on biopsy
 - Assessment of NASH CRN Fibrosis Score at Week 24
 - Assessment of Ishak Fibrosis Score at Week 24
 - Assessment of fibrosis using digital pathology at Week 24
 - Assessment of CPA at Week 24
 - Assessment of fat in stained tissue by morphometry at Week 24
 - Assessment of alpha smooth muscle actin at Week 24
- Assessment of NAS at Week 24
- Assessment of NASH using digital pathology
- Hepatic fat fraction as measured using MRI-PDFF at Week 24 and Week 48
- Noninvasive measures of fibrosis and/or cirrhosis
 - Liver stiffness as determined by MRE at Week 24 and Week 48
 - Noninvasive scores of hepatic fibrosis (APRI, FIB-4, ELF, and NAFLD Fibrosis Score) at Week 24 and Week 48
- Metabolic assessments at Week 24 and Week 48
 - Physical assessments (body weight, waist circumference, and BMI)
 - Serum lipids (LDL, HDL, and TGs)
 - Plasma glucose
 - Plasma insulin
 - Hemoglobin A1c
- Patient-reported outcomes at Week 24 and Week 48
 - EQ-5D-3L questionnaire
 - SF-36 questionnaire
 - CDLQ-NAFLD questionnaire

- Exploratory biomarkers
 - Transaminases
 - ALT normalization (ALT \leq ULN) at Week 24 and Week 48
 - AST normalization (AST \leq ULN) at Week 24 and Week 48
 - ALT at each visit through Week 52/PTFU
 - AST at each visit through Week 52/PTFU
 - Change from Baseline (Day 1 predose) ALT levels at each visit through Week 52/PTFU Visit
 - Change from Baseline (Day 1 predose) AST levels at each visit through Week 52/PTFU Visit
 - PRO-C3
 - Assessment of PRO-C3 levels at each visit through Week 52/PTFU
 - Change from Baseline (Day 1 predose) in PRO-C3 levels at each visit through Week 52/PTFU Visit
 - Assessment of adiponectin at each visit through Week 52/PTFU

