4.5 Exploratory Endpoints

Exploratory endpoints include the following:

- Quantitative measurements of fibrosis and fat on biopsy
 - Assessment of NASH CRN Fibrosis Score at Week 24
 - Proportion of participants with >=2 stage improvement
 - Changes in Fibrosis (as expressed by Shift from baseline)
 - Proportion of participants with >=1 stage improvement, no change, or worsening
 - Assessment of Ishak Fibrosis Score at Week 24
 - Proportion of participants with >=2 stage improvement
 - Changes in Fibrosis (as expressed by Shift from baseline)
 - Proportion of participants with >=1 stage improvement, no change, or worsening
 - Assessment of Fibrosis and NASH using digital pathology at Week 24
 - Absolute, percent change, and change from baseline
 - Assessment of CPA at Week 24
 - Proportion of participants with any improvement
 - Absolute, percent change, and change from baseline
 - Assessment of fat in stained tissue by morphometry and alpha smooth muscle actin (SMA) at Week 24
 - Absolute, percent change, and change from baseline
- Assessment of NAS score at Week 24
 - Changes in NAS (as expressed by shift from baseline, for each individual NAS components (Steatosis, inflammation, Ballooning) as well as Total score)

Sponsor: Bristol-Myers Squibb

[figure not shown]
Protocol no: MB130-068

- Proportion of participants with improvement, no change, or worsening in NAS Total
- Assessment of NASH using digital pathology
 - Absolute, percent change, and change from baseline
- Hepatic fat fraction as measured using MRI-PDFF at Week 24 and Week 48
 - Absolute, percent change, and change from baseline
 - Proportion of subjects in each treatment group with $\geq 30\%$ relative reduction, $\geq 20\%$ relative reduction, $\geq 10\%$ relative reduction, and $\geq 5\%$ absolute reduction
- Noninvasive measures of fibrosis and/or cirrhosis
 - Liver stiffness as determined by Magnetic Resonance Elastography (MRE) at Week 24 and Week 48
 - Absolute, percent change, and change from baseline
 - Proportion of subjects in each treatment group with $\geq 19\%$ or $\geq 15\%$ reduction
- Noninvasive scores of hepatic fibrosis (AST-Platelet Ratio Index (APRI), Fibrosis 4 (FIB-4), Enhanced Liver Fibrosis (ELF), and NAFLD Fibrosis Score) from Day 1 to Week 24 and Week 48
 - Absolute, percent change, and change from baseline
 - Proportion of participants in each ELF category by time point
- Metabolic assessments at Week 24 and Week 48

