6.4 Exploratory Analyses

Analyses for exploratory endpoints will be performed using the mITT or safety populations.

Exploratory dichotomous response variables will be summarized in a manner similar to that used for the secondary efficacy analyses. In addition, summaries of ≥ 1 stage improvement, no change, and worsening will be tabulated and graphically presented for NASH CRN Fibrosis Score, Ishak Fibrosis Score, and NAS Total at Week 24. For these analyses, participants without a Week 24 or ET result will be classified into the "Worse" category for these exploratory summaries.

Early termination visits for non-biopsy endpoints such as imaging and biomarkers may occur at other time points and will not be summarized together with Week 24. For non-biopsy endpoints, ET will be summarized separately in the summary tables. Imputation on missing data will not be performed for non-biopsy endpoints.

Summary statistics will be tabulated for all treated subjects by treatment and by Visit. Continuous data will be summarized using n, mean, standard deviation, median, minimum, and maximum.

Analysis of covariance (ANCOVA) model will be used to explore change from baseline for endpoints having a baseline and a post-baseline values.

Repeated measures analysis will model the change from baseline for the endpoint in presence of repeated measurements taken at various timepoints on/before the analysis visit.

Sponsor: Bristol-Myers Squibb

Protocol no: MB130-068

The model will include treatment group, visit, baseline value, treatment * visit and baseline stratification factors as main effects. An unstructured covariance matrix will be used to represent the correlation of the repeated measures within each subject. The model will provide point estimates, standard errors and 2-sided 95% confidence intervals for mean change from baseline at by time points.

Other biomarkers will be descriptively summarized by time point and will include percent change from baseline in addition to change from baseline. Exploratory endpoints assessing relationships will be graphically presented.

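### FIB-4 and APRI are compared only at Weeks 24 and 48 although their inputs are measured at every visit, so participants who stop before Week 24 add nothing to those comparisons

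*Protocol*

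**What the plan says.** **When the scores are endpoints.** Protocol 9.4.4 lists "Noninvasive scores of hepatic fibrosis (APRI, FIB-4, ELF, and NAFLD Fibrosis Score) at Week 24 and Week 48". SAP 4.5 gives the same time points: "NAFLD Fibrosis Score) from Day 1 to Week 24 and Week 48". Protocol 8.5.1 schedules the assessments as "NAFLD Fibrosis Score) at Day 1, Week 24, and Week 48 (or the ET Visit, if applicable", so an early stopper does have a score at the ET Visit.

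**When the inputs are measured.** Protocol 8.5.4 takes the inputs from the safety laboratory values, which "will also be used to determine FIB4 index, APRI, and NAFLD Fibrosis Scores according to the schedule in Section 1". FIB-4 uses age, AST, ALT and platelets; APRI uses AST and platelets (Protocol Appendix 9, SAP 8.10). Table 8 in Protocol 8.5.4 has "Hematology (to be collected at each visit through the Week 52/PTFU Visit", which supplies platelets, and sets the same frequency for blood chemistry, which supplies AST and ALT. SAP 4.5 analyses ALT and AST in their own right at each of those visits.

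**How early stoppers are handled.** SAP 6.4 does not combine ET with Week 24 for non-biopsy endpoints: "For non-biopsy endpoints, ET will be summarized separately in the summary tables. Imputation on missing data will not be performed for non-biopsy endpoints". Its repeated-measures model takes measurements up to and including the analysis visit. SAP 8.10 allows a missing score component to be replaced only by a value within 3 days.

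**Liver tests and stopping.** Protocol 8.3.9.1 includes among the reasons to stop study medication "Abnormal liver tests as defined in" Section 8.5.3.1.

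**The concern.** A repeated-measures model deals with dropout by using what was observed before the participant left. For FIB-4 and APRI at Week 24 the plan gives it nothing to use, because there is no earlier post-baseline score. The Week 24 analysis then reduces to a comparison of participants who have a Week 24 value. The earlier inputs exist and are analysed elsewhere in the same plan.

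Two things are at stake. Information from early stoppers is lost, which widens the intervals. In addition, AST and ALT are part of the liver-test stopping rule and are also components of the scores, so stopping may be related to interim values that the model never sees.

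**Working it through.** The plan states no figure for these endpoints, so there is nothing to reproduce. The check is a count of usable records, a variance calculation, and the formulae applied to an enzyme rise.

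**1. Records per participant.** Post-baseline on-treatment visits are Weeks 4, 8, 12, 16, 20, 24, 32, 40 (Protocol 8.4.2) and 48, nine in all. The endpoint lists use two of them.

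| Last scheduled visit completed | Scores at Weeks 24/48 | Scores if derived at every visit |
|---|---|---|
| Week 4, 8, 12, 16 or 20 | 0 | 1, 2, 3, 4 or 5 |
| Week 24, 32 or 40 | 1 | 6, 7 or 8 |
| Week 48 | 2 | 9 |

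The separately tabulated ET score is not counted. The documents give no dropout rate. If 10% or 20% stopped before Week 24, then 197 × 0.10 ≈ 20 or 197 × 0.20 ≈ 39 participants would be absent from the Week 24 comparison.

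**2. Precision.** Assumptions: a fraction m is missing at Week 24, with m/5 stopping after each of Weeks 4, 8, 12, 16 and 20. V is the 6 × 6 correlation matrix of the scores at Weeks 4 to 24, and V_j is its leading j × j block.

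- Week 24 values only: variance = 1/(1 − m), in units of residual variance divided by the number of participants.
- All visits, by generalised least squares: information I = (1 − m)V⁻¹ + Σ (m/5)V_j⁻¹ for j = 1 to 5, each V_j⁻¹ padded with zeros to 6 × 6. The variance of the Week 24 mean is the last diagonal element of I⁻¹.

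With Week 24 values only, the variance is 1.1111 at m = 10% and 1.2500 at m = 20%. With all visits:

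| Assumed correlation | m = 10% | Cut | m = 20% | Cut |
|---|---|---|---|---|
| Exchangeable 0.4 | 1.0829 | 2.5% | 1.1857 | 5.1% |
| Exchangeable 0.6 | 1.0586 | 4.7% | 1.1310 | 9.5% |
| Exchangeable 0.8 | 1.0307 | 7.2% | 1.0685 | 14.5% |
| AR(1), lag-one 0.7 | 1.0893 | 2.0% | 1.1982 | 4.1% |
| AR(1), lag-one 0.8 | 1.0746 | 3.3% | 1.1647 | 6.8% |
| AR(1), lag-one 0.9 | 1.0483 | 5.7% | 1.1060 | 11.5% |

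The cut is 2.0-14.5%. Confidence intervals would be shorter by 1 − √(1 − 0.020) = 1.0% to 1 − √(1 − 0.145) = 7.5%. If one sixth of the stoppers leave before any post-baseline visit (m/6 in each group, j = 0 to 5), the cut is 1.6-12.5%.

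**3. Direction of any bias.** FIB-4 is proportional to AST/√ALT and APRI to AST.

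| Rise | FIB-4 multiplied by | APRI multiplied by |
|---|---|---|
| AST and ALT both ×3 | 3/√3 = 1.73 | 3 |
| AST only ×3 | 3 | 3 |
| ALT only ×3 | 1/√3 = 0.58 | 1 |

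Losing participants with enzyme rises can therefore move mean FIB-4 either way.

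**The case against.** The strongest reply is that nothing here is contradictory or undefined. Scoring at Weeks 24 and 48 matches MRE, MRI-PDFF and ELF, and Week 24 is also the biopsy time point. ALT and AST are analysed at every visit and platelets are summarised by visit, so the component data from early stoppers are reported. These are exploratory endpoints, and SAP 6.4 does not say which of them go into ANCOVA and which into the repeated-measures model. All of this stands, and it limits the weight of the point. It does not restore early stoppers to the between-arm score comparison.

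Three stronger readings are tempting, and the documents do not support them.

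- *Early stoppers vanish from the scores.* They do not. An ET score is scheduled and tabulated, and anyone who stops after the Week 24 visit keeps a Week 24 value.
- *The scores are biased towards improvement in any arm with liver-related stopping.* This is not shown. The aminotransferase scenario in Protocol 8.5.3.1 also needs a bilirubin or INR rise, or new signs and symptoms. It allows temporary interruption, after which a Week 24 score is still possible. An ALT-only rise lowers FIB-4. Which arm would be affected more is also unknown: Table 4 predicts ALT falls of 16.7-26.7% on the drug, so enzyme-driven stopping could be commoner on placebo.
- *An all-visit model would remove the bias.* It would do so if stopping depended only on earlier scores. Bilirubin, INR and symptoms are not in a FIB-4 or APRI model, and SAP 8.1 keeps unscheduled repeat tests out of the analysis apart from baseline use. A simulation that stops people on the score alone gives an unbiased result by construction and does not represent the protocol's rule.

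**Conclusion.** The point holds as a modest, avoidable loss of information. Participants who stop before Week 24 are left out of the FIB-4 and APRI comparisons at Weeks 24 and 48 despite one to five visits of complete inputs. The estimated cost is about 2-15% in the variance of the Week 24 mean. That range rests on an assumed 10-20% missing at Week 24, stopping spread evenly over Weeks 4-20, and assumed correlations of 0.4-0.9; the documents give none of these.

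The plan also prevents the model from using interim values that may be related to stopping. Whether this causes a material bias, and in which direction, cannot be settled from the documents. It is reasonable to infer that ET scores stay out of the models because they are summarised separately, but the SAP does not say so. The change is worth making because it is cheap; conclusions about the primary endpoint do not depend on it.

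**What to change.** In SAP 4.5, derive FIB-4 and APRI at every scheduled visit through Week 52/PTFU with the formulae already in SAP 8.10. In SAP 6.4:

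- Name the repeated-measures model for these two scores and enter all scheduled on-treatment visits, with the terms already planned.
- State whether an ET value is mapped to the nearest scheduled visit or kept out of the model.
- Keep Weeks 24 and 48 as the reported time points.

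Leave ELF and the NAFLD Fibrosis Score as planned, because the ELF markers and the weight needed for BMI are not collected at every visit.

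The cost is SAP wording and programming, with no new samples or visits. The downsides are more time points in the tables and a larger unstructured covariance matrix: 6 × 7/2 = 21 parameters through Week 24 and 9 × 10/2 = 45 through Week 48, against 2 × 3/2 = 3 for the two-visit version. A fallback covariance structure should be named in case that model does not converge.
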